### **4.3 Secondary Endpoints**

**Adherence**

- Frequency of study IVR removal/expulsions (voluntary and involuntary) and duration without IVR in vagina (by self-report)
- IVR use initiation and persistence (whether the IVR is in place when participants come to the clinic for their study visits)

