### **10.7.3 Secondary Analyses**

#### **Adherence Analysis**

To assess participant adherence to the IVR, the proportion of participants who reported keeping the study IVR inserted at all times during the 91 days will be calculated along with a 95% confidence interval. (Clinician-initiated VR removals for the purpose of clinical examination will be excluded from consideration during product adherence analysis.) For participants who were not fully adherent, the number of self-reported removal/expulsion events and average duration of these events will be reported. Additionally, the average cumulative period of time during the study period when the study IVR was outside the vagina will be calculated. Number, type and circumstances of expulsions (voluntary and involuntary) will be described.

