5. GENERAL ANALYSIS METHODS

Descriptive statistics will be used to assess group characteristics or difference by study arm. Continuous variables will be summarized using the number of non-missing values, mean, standard deviation, median, interquartile range (IQR), and range (minimum and maximum). Categorical variables will be summarized using the number of missing values, frequencies, and percentages. The Pearson-Clopper method¹ will be used to obtain 95% confidence intervals on the proportion of binary variables where applicable.

Within-treatment group assessment of the change from the baseline measurement to a follow-up measurement will be analyzed using McNemar's test (for categorical response variables) or the paired t-test or Wilcoxon signed-ranks test (for continuous variables).

When use of formal testing to assess differences between arms is required, the following methods will be used: Fisher's exact test or logistic linear regression for categorical response variables; t-test or linear regression for continuous outcomes. Hypothesis tests for the primary and secondary endpoints comparing the two study arms (active and placebo IVR arms) will have a two-sided significance level of 5%.

To assess the adequacy of the randomization, participants in each of the two arms will be compared for baseline characteristics including demographics and laboratory measurements using descriptive statistics. Due to the small sample size, formal comparisons will not be done.

In any situation with missing data, appropriate secondary analyses will be performed to adjust for variables that may be related to the missingness mechanism. If missing data rates are higher than 10%, covariates that are related to missingness in likelihood-based regression models will be included. A sensitivity analysis to assess the potential impact of the missing data will also be performed. These analyses will include imputing the data under the most extreme scenarios of information missingness,

such as assuming everyone missing has an extreme value of the missing variable, and less informative imputation approaches.

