9. SECONDARY ENDPOINT ANALYSES

9.1 Adherence Secondary Endpoint

To assess participant adherence to the IVR, the proportion of participants who reported keeping the study IVR inserted at all times during the 91 days will be calculated along with a 95% confidence interval, using the exact Pearson-Clopper method, and these proportions will be formally compared using Fisher's exact test. Adherence will be calculated using the self-reported IVR outages from the Ring Adherence eCRF and clinician-reported outages reported on the Study Termination, the Discontinuation of Study Product, the Product Hold Log, and the Ring Insertion and Removal eCRFs. Clinician-initiated IVR removals for the purpose of clinical examination will be excluded from consideration during product adherence analysis.

For participants who were not fully adherent, the number, median, and IQR of the duration of self-reported removal/expulsion events will be reported. Additionally, the median and IQR of the cumulative time during the study period when the study IVR was outside the vagina will be calculated. No formal statistical comparisons will be performed.

Additional summaries of the number and proportion of participants who had the vaginal ring in place at the start of the visit, who had the ring removed at the visit, who had a ring inserted at the visit, and the reasons for removals from the Ring Insertion and Removal eCRF will be tabulated by arm. The following information collected on the Ring Adherence eCRF will be tabulated for all follow-up visits, overall and by arm: the total number of times that the participant had the vaginal ring out; the number of times that the participant had the vaginal ring out for more than 12 hours continuously (grouped in following categories: 0, 1, 2, 3 or more), the longest number of days in a row the vaginal ring was out; the number and proportion of participant visits where the ring was removed; the number and proportion of participant visits where the ring came out on its own; the number and proportion of participant visits reporting the different reasons why the vaginal ring was removed and the reasons why the vaginal ring came out on its own. No formal statistical comparisons will be performed.

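### SAP 9.1 counts clinician-directed holds and discontinuations as outages, so the adherence proportion and its between-arm test mix participant behaviour with safety management

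*SAP*

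**What the plan says.** Protocol 4.3 has two adherence endpoints. The first covers removals and expulsions and "duration without IVR in vagina (by self-report"). The second is whether the ring is in place at clinic visits, and it carries no self-report label. Protocol 10.7.3 analyses "the proportion of participants who reported keeping the study IVR inserted at all times during the 91 days" with a 95% confidence interval, and specifies no comparison between arms.

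SAP 9.1 repeats that definition and then sets the sources: self-reported outages from the Ring Adherence eCRF, together with "clinician-reported outages reported on the Study Termination, the Discontinuation of Study Product, the Product Hold Log, and the Ring Insertion and Removal eCRFs". It makes one exception: "Clinician-initiated IVR removals for the purpose of clinical examination will be excluded from consideration during product adherence analysis". It adds that "these proportions will be formally compared" by Fisher's exact test. SAP section 5 makes between-arm tests of primary and secondary endpoints two-sided at the 5% level.

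Protocol 9.4 requires a hold for a Grade 3 event judged related to product and for any Grade 4 event, unless the event is specifically addressed elsewhere. Protocol 9.6 requires one for deep epithelial disruption.

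**The concern.** Adherence asks whether participants used the ring as directed. A participant whose ring is held for an adverse event is following direction, yet SAP 9.1 places that hold in the same numerator and the same test as a voluntary removal. If holds are more frequent in the TFV arm, part of any adherence difference reflects safety management, and the reported proportion does not show how much.

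SAP 9.1 also does not fit together internally. Participants are classified from self-report and clinician forms, but the first duration summary for those not fully adherent covers self-reported removal and expulsion events only. Someone classified solely through the Product Hold Log may have no such event. The cumulative-time summary does not say whether time after a discontinuation counts.

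**Working it through.** **Which outages count**

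| Source named in SAP 9.1 | What it can carry | Exempt? |
|---|---|---|
| Ring Adherence eCRF | Self-reported removals and expulsions, with reasons | No |
| Product Hold Log | Holds, with reasons, resolution and duration (SAP 10.1) | No |
| Discontinuation of Study Product | Adverse event, allergic reaction, pregnancy, sponsor termination; also refusal, withdrawal of consent, unwillingness to comply, loss to follow-up (SAP 6.3) | No |
| Study Termination | Largely overlapping reasons (SAP 6.3) | No |
| Ring Insertion and Removal | Removals at visits, with reasons (SAP 9.1) | Examination removals only |

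The clinician forms therefore hold both clinician-directed and participant-driven stops. SAP 9.1 does not separate them, although the reasons are recorded.

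**The plan's own figure**

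Protocol 10.4.2 states a precision of 13.0% (half the width of the 95% interval) for 48 participants at 75% observed adherence. The exact Clopper-Pearson interval for 36/48 is 60.4% to 86.4%, a half-width of 12.98 points. The stated figure reproduces.

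**Effect of counting holds**

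Inputs: 32 active and 16 placebo participants (protocol 10.1); 75% adherence (protocol 10.4.2), applied here to both arms as an assumption, giving 24/32 and 12/16; and h, the number of otherwise adherent TFV participants with a clinician-directed hold or discontinuation, with none assumed on placebo. The documents give no value for h.

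- Active arm: (24 − h)/32, a fall of 1/32 = 3.1 points per participant.
- Pooled: (36 − h)/48, a fall of 1/48 = 2.1 points per participant.
- Test: two-sided Fisher's exact test of (24 − h)/32 against 12/16.

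| h | Active arm | Exact 95% CI, active | Pooled | Fisher p |
|---|---|---|---|---|
| 0 | 24/32 = 75.0% | 56.6% to 88.5% | 36/48 = 75.0% | 1.00 |
| 3 | 21/32 = 65.6% | 46.8% to 81.4% | 33/48 = 68.8% | 0.74 |
| 6 | 18/32 = 56.3% | 37.7% to 73.6% | 30/48 = 62.5% | 0.34 |
| 10 | 14/32 = 43.8% | 26.4% to 62.3% | 26/48 = 54.2% | 0.065 |
| 11 | 13/32 = 40.6% | 23.7% to 59.4% | 25/48 = 52.1% | 0.034 |

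Six such participants move the pooled estimate by 75.0 − 62.5 = 12.5 points, nearly the whole stated precision of 13.0. The test responds far more slowly than the estimate.

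**The case against.** The strongest reply is that the protocol does the same. It has the same single exclusion (7.9, 10.4.2, 10.7.3) and nowhere exempts holds. Section 10.4.2 describes the measure without any self-report qualifier, 7.9 captures adherence by CASI and CRFs, and the second endpoint in 4.3 is not self-reported. A participant whose ring was held could not truthfully report that it stayed in throughout, so a purely self-reported analysis would probably score her the same way. All of this stands. A reader might infer that the SAP contradicts the protocol on how holds are treated; the documents do not support that. The departure is limited to the clinician-form sources and the Fisher's test that 10.7.3 lacks.

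A second reply is that the clinician forms also record real non-adherence, such as refusal of product or withdrawal of consent. This also stands, and it rules out simply reverting to self-report. That would miss such stops, and could score someone taken off the ring early as having kept it in for 91 days.

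Third, counting every outage is a defensible measure of continuous use, which is how the objective is framed. It is, and it should be kept under its own name.

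Fourth, holds, discontinuation reasons and adverse events are tabulated separately (SAP 6.3, 8.2, 10.1). Toxicity would therefore not be hidden. But those are marginal tables. They do not show how many of the participants scored non-adherent were so only because of a hold, so the behavioural proportion cannot be recovered from them.

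Finally, a reader might take an expected hold rate from the terminated TDF ring study in protocol 2.4.3. That is a different product and supports no rate here. In the A13-128 study of the TFV ring, no adverse event led to discontinuation, though use lasted only 16 to 18 days.

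**Conclusion.** The point holds in a limited form. As written, SAP 9.1 lets clinician-directed holds and discontinuations lower the adherence proportion and enter its between-arm test. This rests on the plain reading of the source list and its one exception; the SAP does not say in so many words that a held participant is non-adherent.

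The cost is 3.1 points of active-arm adherence per affected participant, whatever the hold rate. The totals in the table depend on assumed values: 75% adherence in both arms, holds only in the TFV arm, and hold counts chosen for illustration. A reader might infer that a modest excess of holds would produce a significant adherence difference. The arithmetic does not support that, since about 11 of 24 otherwise adherent TFV participants would have to be affected. The harm is mainly to the estimate and its interpretation. This is a secondary endpoint; no primary result, sample size or stated precision is wrong because of it.

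**What to change.** In SAP 9.1, classify each outage by its recorded reason and report two proportions by arm, each with an exact confidence interval.

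1. **Participant adherence:** no participant-initiated removal, no expulsion and no participant-driven stop (refusal, withdrawal of consent, unwillingness to comply) while the participant was directed to use the ring. Leave time under a clinician-directed hold, or after a clinician-directed discontinuation, out of the assessed period, and show how many participants this affects. State the rule for loss to follow-up.
2. **All-cause continuous ring use over 91 days:** all outages counted as now. Do not call this persistence, which protocol 4.3 defines as the ring being in place at visits.

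Apply the Fisher's test to the first proportion. If the second is also tested, label that test as mixing behaviour and safety. Split cumulative time out of the vagina in the same way. Record in the SAP that the clinician-form sources and the between-arm test go beyond protocol 4.3 and 10.7.3, with the reason.

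The cost is wording and about one extra table row. SAP 9.1 already names the forms, and the reasons are already collected.

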9.2 Acceptability Secondary Endpoint

To assess acceptability of the study IVR, the participants' answers to questions J2 ("Overall, how much do you like the ring?"), based on the participants' self-report by CASI at the Product Use End Visit (PUEV) or Early Termination Visit, will be used for this the primary endpoint analysis. The acceptability response is on the 10-point Likert scale and will be summarized by calculating the mean, standard deviation, median, IQR, minimum, and maximum values and 95% CI overall, and by study arm. A bar plot of scores reported for question J2, by arm, will be presented. In addition, acceptability between the active and placebo arms will be compared using the t-test or Mann-Whitney U test depending on the distribution of the data.

10. SAFETY ANALYSES

All participants enrolled will be assessed for safety and tolerability. See section 8.2 for the description of the analyses on the Safety Primary Endpoint Adverse Events. For the additional safety results below, no formal statistical testing will be performed.

10.1 Product Holds

Instances of product hold as collected in the Product Hold Log eCRF will be described. The number and percentages of women who had a product hold at least once, the number of product holds, reasons for product holds, resolution of product hold and duration of product hold (for those who were instructed to resume product use) will be presented in tables by arm and by site.

10.2 Laboratory Evaluations

Boxplots and tables with summary statistics (see Section 5) will be reported for laboratory evaluations performed at the Screening and PUEV (Day 91) Visit, by arm and visit and by site and visit. The following tests will be included: hemogram (hemoglobin, hematocrit, MCV, platelets, WBC, neutrophils, lymphocytes, monocytes, eosinophils, and basophils) test results as collected on the Hematology eCRF and chemistries (AST, ALT, and creatinine) test results as collected on the Chemistry Panel eCRF.

10.3 Pelvic Exam Findings

The summary of abnormal pelvic exam findings will include any findings reported on the Pelvic Exam eCRF at any visit after the Enrollment Visit. The numbers and proportion of participant-visits with any abnormal pelvic exam findings and with specific types of findings will be presented in tables by arm and by site.

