### **5.3 Exclusion Criteria**

Participants who meet any of the following criteria will be excluded from the study:

1) Pregnant at Screening or Enrollment or plans to become pregnant during the study period

*Note: A documented negative pregnancy test performed by study staff is required for inclusion; however, a self-reported pregnancy is adequate for exclusion from the study.*

2) Diagnosed with symptomatic urinary tract infection (UTI) or reproductive tract infection (RTI) at Screening or Enrollment

*Otherwise eligible participants diagnosed with UTI/RTI during screening will be offered treatment. If treatment is complete and symptoms have resolved within the 45 day screening window, eligible participants may be enrolled.*

*Note: Asymptomatic BV and candidiasis are not exclusionary.*

- 3) Diagnosed with an acute sexually transmitted infection (STI) requiring treatment per current Centers for Disease Control and Prevention (CDC) guidelines (<http://www.cdc.gov/std/treatment/>) at Screening or Enrollment such as gonorrhea, chlamydia, trichomonas, pelvic inflammatory disease, and/or syphilis

*Note: Genital warts requiring treatment and frequent recurrence of HSV are considered exclusionary; however, infrequent HSV outbreaks are not. Genital warts requiring treatment are defined as those that cause undue burden or discomfort to the participant, including bulky size, unacceptable appearance, or physical discomfort. See MTN-038 Study-Specific Procedures (SSP) Manual for additional information.*

- 4) Has a clinically apparent Grade 2 or higher pelvic exam finding (observed by study staff) at Screening or Enrollment. \*

*Note: Cervical bleeding associated with speculum insertion and/or specimen collection judged to be within the range of normal according to the clinical judgment of the IOR/designee is considered expected non-menstrual bleeding and is not exclusionary.*

*Note: Otherwise eligible participants with exclusionary pelvic exam findings may be enrolled/randomized after the findings have improved to a non-exclusionary severity grading or resolved within 45 days of providing informed consent for screening.*

- 5) Participant report and/or clinical evidence of any of the following:

- a) Known adverse reaction to any of the study products (ever), including polyurethane
- b) Chronic and/or recurrent vaginal candidiasis
- c) Non-therapeutic injection drug use in the 12 months prior to Enrollment

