8.2 Safety Primary Endpoint

For the analysis of the primary safety endpoints, two tables summarizing the number and the proportion (in percentage) of participants experiencing (i) a grade 2 or higher genitourinary adverse event and (ii) a grade 3 or higher adverse event, will be produced. Each participant will contribute once in each category (i.e., only the highest severity AE for each participant) for the calculation of the proportions. Exact 95% binomial confidence intervals for the proportion of participants experiencing each safety endpoint, using the Pearson-Clopper method, will be provided for each arm. The Fisher's exact test will be used to test for differences in event rates between the TFV IVR arm and the placebo IVR arm.

Additionally, the following listings and tables of AEs will be presented. No formal statistical testing will be conducted:

- A cumulative listing of AE sorted by arm, site, and participant ID.
- Number and percentages of adverse experiences by body system/MedDRA preferred term and severity overall and by arm, and by site.
- Number and percentages of adverse experiences by body system/MedDRA preferred term and relationship to study product overall and by arm, and by site.
- AE summary: the total number of adverse experiences by severity and relationship to study product, overall and for each arm and each site separately.

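### The SAP 10.3 pelvic-finding tables count participant-visits, so on their own they show neither how many participants were affected nor which findings are new since Enrollment

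*SAP*

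**What the plan says.** SAP 10.3 (Pelvic Exam Findings) takes in "any findings reported on the Pelvic Exam eCRF at any visit after the Enrollment Visit". Its output is that the "numbers and proportion of participant-visits with any abnormal pelvic exam findings and with specific types of findings will be presented"; the breakdown is per arm and per site. SAP 10 states that these additional safety results are not formally tested.

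Baseline pelvic findings appear separately in SAP 7.5, as Screening and Enrollment tables by arm and by site. The any-finding count there also uses participant-visits. Neither section cross-classifies a participant's follow-up exam against her Enrollment exam.

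Entry does not require a normal exam. Protocol 5.3, item 4 excludes a participant who "Has a clinically apparent Grade 2 or higher pelvic exam finding (observed by study staff) at Screening or Enrollment". Its note adds that otherwise eligible participants "may be enrolled/randomized after the findings have improved to a non-exclusionary severity grading or resolved within 45 days" of consent for screening. A Grade 1 finding may therefore be present at Enrollment.

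Other parts of the plan bear on the same events:

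- Protocol 8.3.1 records AEs of every grade from randomization.
- SAP 8.2 plans "Number and percentages of adverse experiences by body system/MedDRA preferred term and severity overall and by arm, and by site", and "A cumulative listing of AE sorted by arm, site, and participant ID".
- SAP 10.1 reports "The number and percentages of women who had a product hold at least once", with reasons, by arm and by site.

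**The concern.** For a ring worn for 91 days, the natural safety question about low-grade pelvic findings is how many participants developed one while using it. A participant-visit table answers a different question: at what share of exams a finding was seen. A lasting finding is counted at every exam and a short-lived one once, and a finding that predates the ring is counted like one that arose on it.

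Grade 1 findings matter here because they fall below both primary safety endpoints (Grade 2 or higher genitourinary events; Grade 3 or higher events). Protocol 2.4.3 also describes a trial of a different product, a TDF ring, that was stopped after 8 of 12 participants in the TDF arm developed Grade 1 vaginal and cervical ulceration. Protocol 2.4.3 adds that MTN-038 is the first human study of the TFV ring over its full intended 90 days.

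**Working it through.** The plan states no figure on this point, so there is none to reproduce. The check is how tightly a 10.3 entry fixes the number of participants affected.

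**Inputs**

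- Arm sizes: 32 active, 16 placebo (Protocol 10.1).
- Required follow-up pelvic exams: Visits 3 to 9, that is Days 1, 7, 14, 28, 42, 56 and 91, so seven (Protocol Appendix I). At Visit 10 an exam is done only if indicated.
- Assumption: all seven exams attended and no additional ones.

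**Denominators**

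- Active: 32 × 7 = 224 participant-visits.
- Placebo: 16 × 7 = 112 participant-visits.

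**Bounds**

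If k visits in an arm of n participants are positive, each affected participant accounts for between 1 and 7 of them. The number affected is at least ceil(k/7) and at most min(k, n).

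| Arm | k positive visits | Table entry | Participants affected | As % of arm | Upper ÷ lower |
|---|---|---|---|---|---|
| Active | 1 | 1/224 = 0.4% | 1 | 3.1% | 1 |
| Active | 3 | 3/224 = 1.3% | 1 to 3 | 3.1% to 9.4% | 3 |
| Active | 7 | 7/224 = 3.1% | 1 to 7 | 3.1% to 21.9% | 7 |
| Active | 28 | 28/224 = 12.5% | 4 to 28 | 12.5% to 87.5% | 7 |
| Active | 100 | 100/224 = 44.6% | 15 to 32 | 46.9% to 100% | 2.1 |
| Placebo | 7 | 7/112 = 6.3% | 1 to 7 | 6.3% to 43.8% | 7 |
| Placebo | 28 | 28/112 = 25.0% | 4 to 16 | 25.0% to 100% | 4 |

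The ratio never exceeds 7. It reaches 7 only when k is a multiple of 7 no larger than n, and it shrinks for very small and very large k.

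For k = 7 in the active arm, the two ends also differ in what they say about the true rate. The exact 95% interval is 0.1% to 16.2% for 1/32 and 9.3% to 40.0% for 7/32.

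**Carry-over**

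A participant with a finding at Enrollment that persists through all seven exams adds 7 positive visits and nothing new. Three such participants in the active arm would give 3 × 7 = 21, and 21/224 = 9.4%. In the any-finding row, the same entry fits 21/32 = 65.6% of participants with one new finding each. The documents do not say how many participants have findings at Enrollment, and the number could be zero.

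**What the other outputs recover**

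- AE tables by preferred term (SAP 8.2) cover all grades by arm but, as worded, count adverse experiences. Counting each participant once is specified for the two primary endpoints only.
- The AE listing (SAP 8.2) carries participant ID, so a per-participant count of Grade 1 events can be made from it by hand. Asymptomatic BV, asymptomatic candidiasis and expected genital bleeding are not AEs (Protocol 8.3.1). The documents also give no rule for separating a pre-existing pelvic finding from an AE.
- The product-hold table (SAP 10.1) counts women. Ulceration requires a temporary hold, as does superficial disruption or localized erythema or edema that has worsened or not resolved at re-evaluation (Protocol 9.6). The table gives reasons for holds but is not specified by lesion type, and a superficial finding that resolves quickly needs no hold.

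**The case against.** The best defence is that the plan as a whole handles this. AEs of every grade are recorded from randomization, tabulated by term, severity and arm, and listed by participant. Baseline medical history is listed with severity and ongoing status (SAP 7.2). Ulceration leads to a hold, and SAP 10.1 counts holds per woman. Discontinuations are tabulated per participant with adverse event as a listed reason (SAP 6.3). With 48 participants, counting from a listing is feasible. The share of exams with a finding is also a legitimate summary in its own right, and the rows by finding type narrow the ambiguity. Finally, for epithelial disruption, erythema or edema, Protocol 9.6 calls for early re-evaluation and a hold if the finding does not resolve, so a finding of that kind at all seven exams is unlikely.

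Most of this stands, and it rules out three stronger readings that a reader might infer:

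- That new and carried-over findings cannot be told apart anywhere in the trial. This is true of the 10.3 tables only; the AE listing and the medical history listing offer an indirect route.
- That a repeat of the TDF-ring ulceration would go unseen. Such an event would call for a hold and enter a per-woman count by arm.
- That the table always misstates the number affected seven-fold. Seven is the most it can be under the stated assumptions; at k = 1 there is no ambiguity.

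What the defence does not supply is a planned table of how many participants developed a new Grade 1 pelvic finding, by type and arm.

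**Conclusion.** The point holds for the SAP 10.3 tables. They fix the number of participants affected only within ceil(k/7) to min(k, n), at worst a seven-fold range, and they do not separate findings new since Enrollment from those carried over. New Grade 1 events can be recovered only indirectly, from the AE listing and, for ulceration, from the product-hold table.

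The consequence is limited. The table is descriptive and untested. Arm is randomized, so carry-over and repeated counting add noise and weight to lasting findings rather than an expected bias between arms. The primary safety endpoints are counted per participant and are unaffected, as are sample size and power.

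The bounds assume that all seven required exams are done and no others. Missed exams, Visit 10 exams, or interim and re-evaluation exams would shift them. This is an optional improvement.

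**What to change.** Keep the participant-visit table and add to SAP 10.3, by arm and finding type (including any finding):

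- the number and percentage of participants with at least one post-Enrollment finding that was not present at their own Enrollment exam, or that worsened in grade if the Pelvic Exam eCRF records grade;
- on separate rows, findings carried over from Enrollment.

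The cost is two or three sentences in the SAP and one extra set of rows. Finding type is already tabulated at Enrollment (SAP 7.5) and at follow-up (SAP 10.3), so the new-finding rows need no further data collection and no protocol amendment. The documents do not show whether the eCRF captures grade, so the worsening rule has to be conditional. The one analytic drawback is that matching by type may label a new lesion of the same type as carried over, which is a reason to keep the existing all-findings table beside the new rows.
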